# **CHAPTER 7 DATA MANAGEMENT AND QUALITY**

## **7.1 Data Management**

All data collected for analysis will be de-identified and assigned a unique study number. Any data collected on paper forms will be kept in a locked file cabinet at HRC. Data collected on paper forms will be entered and stored on a password-protected secure server at HRC. When possible, data will be collected directly via our electronic data capture system (e.g., REDCap).

The Institute for Aging Research primarily employs the REDCap system to facilitate data management operations. REDCap is a full-featured clinical trials data management system (DMS) accessible to data entry and data analysis workstations using secure Web technologies. The REDCap product is developed and maintained by Vanderbilt University in cooperation with REDCap Consortium members, including HRC. HSL hosts and maintains a dedicated instance of REDCap for use across our research enterprise. Each research study is provided separate project workspace in which all of the study data are stored in a MySQL relational database on the private corporate network behind several firewalls and located physically within the HSL data center.

## **7.2 Participant Tracking**

Each recruited participant will be tracked closely throughout study enrollment. If desired, a study events calendar will be created for each participant. Any outstanding or incomplete visits will be accessible in real time to the project director and study team. The study team will maintain regular communications with each study participant throughout enrollment, through regularly scheduled follow up calls, and established retention strategies will be used as discussed in §4.7.

# **CHAPTER 8 DATA SAFETY MONITORING PLAN**

## **8.1 Participant Risks**

Participation in this study may be associated with minor risks or safety concerns. The potential risks of this study fall into 5 categories: 1) those related to research participation; 2) those related to testing procedures; 3) those related to the intervention or control products; 4) those related to depressive symptoms; 5) those related to physical activity. The risks are outlined for each category below:

Minor Risk of Participation in Research: With any study, risk of breach of confidentiality is possible since we are collecting personal health information.

Minor Risk of Testing Procedures: The potential risks of the testing procedures are minor since the majority will be questionnaire based assessments. It is possible that participants may find the questionnaires tedious or may be uncomfortable being asked about sensitive topics like suicidality. The participants may also experience pain or bruising that results from the blood draw. With any puncture of the skin, there is an increased likelihood for infection, although this is minor.

Minor Risk Related to Intervention or Control Products: We do not anticipate any major risks for the participants with consumption of either the intervention (freeze dried blueberry powder) or control (placebo powder) products. Participants might grow weary and uninterested in consuming the products each day over the 12-week period. Additionally, the proposed intervention will provide an older adult with 30% of the recommended daily intake of dietary fiber. One may experience side effects that commonly occur with increased dietary fiber consumption if the individual typically consumes relatively low amounts of dietary fiber.

Risk Related to Depressive Symptoms: It is possible that individuals with depressive symptoms may progress in symptom severity during the study period. Although we do not anticipate a change to a more severe category of depression, we recognize that our proposed population of older adults with prevalent depressive symptoms are already predisposed to development of more severe depressive disorders. Importantly, our population of interest is also more likely to experience suicidal ideation.

Risk Related to Physical Activity: Given that our cohort includes older adults who primarily engage in sedentary behavior, a sudden increase in activity may result in musculoskeletal injury and/or exhaustion.

## **8.2 Risk Minimization**

We will attempt to minimize the identified risks as specified below:

Risk Minimization of Participation in Research: To minimize the risk of breach in confidentiality, all primary study data will be recorded with computer tablets on electronic case report forms (CRF) or as digital files generated from laboratory equipment. All data recording will be in accordance with procedures and guidelines outlined in the study's Manual of Procedures (MOP) authored by the study team. Participant confidentiality will be maintained by recording subject data using a unique subject identifier. Identifiable data, such as contact information and medical record numbers, will be recorded and stored separately from the clinical study data. Any paper-based study material and any identifiable data will be kept separate in a locked file cabinet accessible by authorized study staff only. Only the study staff directly responsible for the data collection and the safety of the participant will have access to identifiable information. All electronic CRF data will be stored securely in an electronic data capture and management system. Raw electronic instrumentation data will be organized and saved on a private network file dedicated to the research project. Only those listed on the approved IRB protocol will have access to subject data. Subject data will be coded and locked in a file cabinet in a locked office. Identifying information will not be used during discussion, presentation or research publication. All documents and electronic data will be archived for a minimum of three years, or as required by the IRB and federal regulations, after the completion of the clinical trial. The study will be registered at [clinicaltrials.gov](http://clinicaltrials.gov).

The Hinda and Arthur Marcus Institute for Aging Research employs the Research Electronic Data Capture (REDCap) system for data capture and data management operations. REDCap is a full-featured clinical trials data management system (DMS) accessible to data entry and data analysis workstations using secure Web technologies. While REDCap can be used to collect virtually any type of data (including 21 CFR Part 11, FISMA, and HIPAA-compliant environments), it is specifically geared to support online or offline data capture for research studies and operations. REDCap is developed and

maintained by Vanderbilt University in cooperation with REDCap Consortium members, including HRC. HSL hosts and maintains a dedicated instance of REDCap for use across our research enterprise. Each research project is provided separate workspace in which all of the study data are stored in a MySQL relational database on the private corporate network behind several firewalls and located physically within the HSL data center.

Risk Minimization of Testing Procedures: The majority of the testing procedures will be questionnaire based. Participants will be advised that they can refuse to answer any of the questions. Participants will be permitted to rest between studies to prevent fatigue. To minimize the risk of being uncomfortable during questionnaires on sensitive topics like suicidality, only trained research staff will administer the questionnaires. Research staff will be trained to administer them in a calm, welcoming demeanor and will reassure the participants that the assessment(s) can stop at any time.

To avoid any risk associated with blood draws, only individuals with trained phlebotomist skills will draw blood using standard, sterile safety procedures to minimize risk of infection. Unless performed at the participant's home/residence or other HSL housing facility, blood draws will be done at our study clinic that resides in Hebrew SeniorLife, which is a functioning hospital. Thus, in the rare case a participant needs additional care that the study team is not qualified to provide, the individual will be transferred immediately to the adjacent hospital.

Risk Minimization of Intervention Product: Individuals with allergies to intervention products will not be included in this study to avoid any adverse effects/allergic reactions. We anticipate that the blueberry and placebo powder will be well-tolerated by participants since they consist of dietary nutrients that are regularly consumed. Regardless, every 4 weeks we will ask participants about any complaints or adverse events that are directly related to the study intervention products. We plan to track diarrhea, gas, bloating, abdominal pain, constipation etc. Since the intervention arm will be increasing fiber consumption and sudden changes in fiber intake may cause gastrointestinal distress, participants will be counseled to consume their dietary intervention products alone (i.e. without other foods) to avoid consumption of large quantities of fiber at one time. Since our intervention provides only ~30% of the recommended intake of daily fiber, we do not anticipate this amount will result gastrointestinal distress, if consumed alone. Nevertheless, symptoms of gastrointestinal distress will be captured at each visit and appropriately addressed by the study team. [name], who has a PhD in Nutrition, will consult with participants on their experience with the fiber and reconcile any gastrointestinal stress. If a participant develops a health problem or a potential health problem (in addition to the ones outlined below), the PI will be notified ASAP. If necessary, the SO will be contacted to help decide whether the participant should continue in the study, and/or what further steps regarding medical evaluation should be performed.

Risk Minimization of Depression Severity: Although we do not anticipate a change to a more severe form of depression, we recognize that our proposed population of older adults with prevalent depressive symptoms are already predisposed to development of more severe depressive disorders. The level of depression will be evaluated and monitored at all visits (except for the telephone screen) to proactively monitor participant safety. If at any time during the study an individual's assessments indicate they have progressed to a more severe forms of depression, then specific safety protocols will be followed (e.g., notifying the study psychiatrist and/or PI). Our population of interest is also more likely to experience suicidal ideation, which will also be monitored at every visit to identify any individuals, who may need psychiatric care outside this study. If the participant is deemed to be dangerous or at imminent risk of harm, study staff will contact emergency services (i.e., #911) for immediate medical assistance.

Risk Minimization Related to Physical Activity: Throughout the intervention, study staff will ask participants to report any symptoms, injuries, or adverse events. Any relevant symptoms or adverse events will be monitored throughout the study, and reported to regulatory agencies per their respective reporting guidelines. If participants report a musculoskeletal injury and/or exhaustion, they will be advised to reduce physical activity until the injury has resolved. If

necessary, participants will be recommended to seek medical attention. The PI may consult the SO, to determine what further steps regarding medical evaluation should be performed.

General Risk Minimization: The proposed protocol requires 5 visits over a total 14 weeks and therefore imposes a moderate amount of participant burden with respect to time and effort. Our institute has a strong track record of successful clinical research requiring similar participation, and retention has been high in these projects. The Clinical Research Laboratory at the Marcus Institute is located near a cafeteria and rest room, and is equipped with comfortable seating, a TV, movies, books, and magazines to keep individuals occupied during rest periods. Several additional strategies will be employed to minimize participant burden and maximize adherence to the protocol. We will:

- Develop a personal relationship between participants and members of the staff.
- Schedule appointments at convenient times with familiar staff.
- Explain to participants all aspects of their participation and follow up. We will demonstrate and practice study procedures before beginning data collection.
- Provide reminders of all appointments and follow-up phone calls.
- Include personal notes in the participant's data file to remember events in the life of the participant; these can be commented on at the next visit (e.g., birthday, birth of a grandchild).
- Provide snacks and lunch during all visits.
- Provide transportation for all visits, if required.
- Provide valet or dedicated on-site parking spaces.
- Compensate participants for visits.

### **8.3 Quality Assurance and Safety Monitoring**

The Principal Investigator (PI) will assume primary responsible for ensuring participants' safety on a daily basis. Since this is a single-site, phase 1 pilot study, without high risk, our study will not require an official Data and Safety Monitoring Board (DSMB). However, to ensure and monitor participant safety, a study psychiatrist will oversee all possible adverse events and we will also have a Safety Officer (SO) designated for this study, who resides in the Boston area.

The PI, study psychiatrist, and SO will meet at least twice per year, either in-person or by teleconference call to review study progress, data quality, and participants safety. They will discuss any reported AE's of the participant. The SO will be provided a detailed Data Safety and Monitoring Report of study progress, data, and safety issues.

The Data and Safety Monitoring Report will include 1) recruitment and participant status, 2) reasons for screening failure, 3) any protocol deviations, 4) participant demographics, and 5) all reports of AE's and unanticipated problems. For each AE/unanticipated problem, report will be generated that includes the participants age, sex, medical history, related symptoms, and descriptions of the AE/unanticipated problem.

The responsibility of the SO includes (but is not limited to) data and safety monitoring, advising the NIA Program staff and the Principal Investigator (PI) regarding participant safety, study risks and benefits, scientific integrity, participant recruitment, and ethical conduct of a study. Prior to the intervention period, SO will review the entire IRB-approved study protocol regarding subject safety and analysis, the informed consent documents regarding applicability and readability, and participant recruitment and retention milestones.

### **8.4 Adverse Event Collection and Reporting**

Any adverse or serious adverse events will be logged using forms either provided by or modeled after the forms that are provided by the NIA Clinical Research Toolbox .

#### **Adverse Event Definition and Categorization**

An adverse event is any untoward medical occurrence in a participant, whether or not it is causally related to the study. An adverse event can therefore be any unfavorable and unintended sign (including an abnormal laboratory finding, for example), symptom or disease temporally associated with the study. We have defined

specified thresholds of change in some of our assessments (e.g., change in depressive symptom severity or change in related symptom severity) that will qualify as an adverse event which is outlined in our manual of procedures. All adverse events will be recorded on the appropriate case report forms and source documents. The PI, study psychiatrist, and/or trained staff member will evaluate all adverse events as to their severity and relation to the test article. The severity of adverse events will be graded as follows:

Mild: Awareness of a sign or symptom but easily tolerated.

Moderate: Discomfort sufficient to cause interference with usual activity or to affect clinical status.

Severe: Incapacitating with inability to do usual activity or to significantly affect clinical status.

Life Threatening: The participant was at immediate risk of death from the adverse event as it occurred.

The Investigator will also assess the relationship of any adverse event to the study, based upon available information, using the following guidelines:

0 = Unlikely: No temporal association, or the cause of the event has been identified

1 = Possible: Temporal association, but other etiologies are likely to be the cause; however, involvement of the study procedures cannot be excluded.

2 = Probable: Temporal association, other etiologies are possible, but not likely.

To determine the attribution and temporal association of an adverse event we will consider the following:

1) Whether the participant reports they have experienced the same symptom prior to the study intervention.

2) Whether the symptom occurred and resolved within 24 hours of taking the study intervention.

The PI, study psychiatrist, and/or SO will consider the symptom according to the conditions stated above and determine temporality as per clinical judgment.

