**3-Day Diet Records:** Diet records (consisting of 2 weekdays and 1 weekend day) will be reviewed by research staff for accuracy and completeness. Records will be entered into a dietary analysis program (e.g., Nutrition Data System for Research) to estimate dietary intake of nutrients.

**Height/Weight** will be measured at the baseline visit.

1. Height will be measured using a stadiometer.
2. Weight will be measured using a digital Health-o-meter scale.

**Vital Signs** (e.g., body temperature, pulse, and seated blood pressure) will be measured at the baseline visit. After 3-5 minutes of rest, seated blood pressure will be measured twice with an automated cuff.

**Motives for Physical Activities Measure-Revised (MPAM-R):** Motivation to engage in physical activity will be assessed with the MPAM-R, which is a self-report questionnaire has been used in middle-aged and older adults.

**Blood (up to 10 mL)** will be collected by a trained phlebotomist using sterile procedures. Blood will be processed and stored at -80 degree C for future analyses. Batch analyses of relevant inflammatory markers (e.g., C-reactive protein, interleukin-6, and brain-derived neurotrophic factor) will be measured by a reputable lab (e.g., Quest or collaborators at the University of Connecticut).

**Relevant Symptoms:** Information on relevant symptoms including gastrointestinal distress, appetite, pain etc., will be collected by self-report.

**Compliance:** Compliance with our dietary intervention will be evaluated throughout the study. Participants will be asked to log consumption of their powder and keep all of their used powder packets. At the study visit, participants will return all unused and used powder packets to estimate number of intended doses that were consumed.

**Week 4 Mid-point Visit (~45 minutes):** The Week 4 Mid-point Visit will include an evaluation of motivation, depression level (PHQ-9), suicidal ideation, relevant symptoms and compliance. Participants will again be asked to continue to wear the ActiGraph and provided with new 3-day diet records to fill out the week prior to their next visit.

**Week 6 Mid-point Visit (~45 minutes):** The Week-6 Mid-point Visit will be the same as Week 4 Mid-point Visit, but it will also include turning in diet records, a blood draw of ~10 mL, as well as an evaluation of vitals and social network.

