### 5.3 Dietary Intervention

The duration of this study will be a total of 14 weeks. The first two weeks will require participants to avoid eating certain foods (e.g., fiber- and anthocyanin-rich foods) while also monitoring their usual physical activity with the ActiGraph just prior to the intervention period.

Individuals will then be randomized to either the intervention or the control group. This is a double-blinded study, so the study staff nor the participant will know what powder the participants are assigned to. Those randomized to the intervention group will be asked to consume approximately 48 g of freeze-dried blueberry powder as a source of ~8 g of fiber and 600 mg of anthocyanins. The proposed dose of 48 g of freeze-dried blueberry powder is equivalent to approximately 2 cups of whole blueberries. Individuals randomized to the control group will be asked to consume approximately 48 g of a nutritionally matched placebo powder that is devoid of anthocyanins and fiber.

The powders will be individually packaged in 24 g amounts. Participants will be instructed to consume 2 packets of their respective powder each day for 12 weeks. Participants will be provided with suggestions/recipes on how to consume the powder (for example, mixed in 12 fl oz of water or mixed in 12 fl oz of almond milk). At the beginning of the study the participants will be given a sample of materials (e.g., mixing apparatus) or ingredients (e.g., almond milk) that participants will be able to use to make the suggested recipes they were provided with. It is recommended that participants consume their powder all at once. Given that intervention and control products are regularly consumed, we do not anticipate any toxicities.

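### Under daily dosing, an effect that persists cannot meet the 24-hour attribution factor in Section 8.4, and the prior-symptom factor cannot register worsening

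*Combined protocol and SAP*

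**What the plan says.** Section 8.4 (Adverse Event Definition and Categorization) names two things to consider when deciding attribution and temporal association:

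- Factor 1: "Whether the participant reports they have experienced the same symptom prior to the study intervention".
- Factor 2: "Whether the symptom occurred and resolved within 24 hours of taking the study intervention".

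The PI, study psychiatrist and/or Safety Officer weigh the symptom against these conditions and "determine temporality as per clinical judgment". On the relatedness scale, grade 0 (Unlikely) is defined as "No temporal association, or the cause of the event has been identified"; both higher grades, Possible and Probable, require a temporal association.

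The same section says that set thresholds of change in some assessments count as adverse events, giving as examples "change in depressive symptom severity or change in related symptom severity". The thresholds themselves are in the manual of procedures, which is not among the documents.

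On exposure, Section 5.3 says: "Participants will be instructed to consume 2 packets of their respective powder each day for 12 weeks". It recommends taking the daily amount in one go. On expected symptoms, Section 8.2 says: "We plan to track diarrhea, gas, bloating, abdominal pain, constipation etc". It links sudden changes in fiber intake to gastrointestinal distress.

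**The concern.** A requirement that a symptom both begin and end within 24 hours of taking the product suits a single or occasional exposure. Here exposure is continuous. A real product effect may last as long as dosing lasts, and factor 2 gives a rater no support for calling such an effect temporally associated. Factor 1 has a different gap: it asks whether the symptom was ever there before, not whether it has become worse.

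The grade matters in three places. Under Section 8.4, at least possible relatedness is one of three joint conditions for the 2-week report to the IRB, NIA program officer, Safety Officer and OHRP. It is also required for serious adverse events to fall under the 10-day report to the IRB. Under Section 8.5, a serious event thought to be directly related to study products or procedures ends the participant's involvement. If the written factors pull grades down for sustained or worsening events, those are the routes that could be weakened.

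**Working it through.** The plan gives no figure on this point, and no sample size or power quantity enters, so the check sets the texts side by side.

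**Step 1: the onset half of factor 2.** Daily dosing for 12 weeks is 12 × 7 = 84 dosing days. With the powder taken once a day, consecutive doses are about 24 hours apart. In a compliant participant, almost any onset after the first dose is therefore within 24 hours of the latest dose. This half is met nearly automatically and separates nothing.

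**Step 2: the resolution half.** Only this half can tell one event from another. By its wording, any event lasting more than 24 hours fails it, whatever its cause.

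**Step 3: both factors applied to typical events.** The section states no direction for either factor. The table takes the natural reading: no prior occurrence, and onset with resolution inside 24 hours, each point toward relatedness.

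| Event | Factor 1 | Factor 2 |
|---|---|---|
| New and short-lived, such as gas that passes the same day | No prior occurrence: supports | Met: supports |
| New and sustained, such as constipation over several days | No prior occurrence: supports | Onset met, resolution not: no support |
| Sustained worsening of a symptom present at entry, such as low mood | Prior occurrence, however large the worsening: no support | Not met: no support |

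The third row is relevant to this population. Section 3.3 requires depressive symptoms at entry, and Section 8.1 names their progression as a risk.

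**Step 4: consistency with the plan's own event definitions.** Table 1 schedules the PHQ-9 and relevant symptoms at baseline and weeks 4, 6, 8 and 12, so consecutive assessments are 2 to 4 weeks apart. An adverse event defined by a change in severity between two such visits cannot be shown from the visit records alone to have come and gone within a day. The plan thus recognizes events through change in severity but lists no factor that uses change in severity to attribute them.

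**Step 5: data available for a better factor.** Baseline PHQ-9 is collected. So are baseline symptoms (Section 5.2: "Information on relevant symptoms including gastrointestinal distress, appetite, pain etc., will be collected by self-report"). Section 5.2 also has participants log powder consumption and return used and unused packets, so gaps in dosing can be seen.

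**The case against.** The strongest reply is that these are two prompts, not an algorithm. Section 8.4 has the assessors consider them, bases relatedness on available information, and leaves temporality to clinical judgment. Nothing forces Unlikely, and Possible remains open for a sustained event. This stands, and it limits the point to a nudge. It does not remove the point, because the assessors are told to judge with reference to these conditions and no others are listed.

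A reader might infer that both factors suit only short-lived reactions. The text does not support that. Factor 1 has no link to duration and makes a crude comparison with the pre-intervention state. It works for new symptoms, including suicidal ideation (current ideation is excluded at entry) and new injury.

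A reader might also infer that important harms would go unreported. That is not supported either:

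- The 2-week report also requires the event to be unexpected. Fiber side effects, progression of depressive symptoms and musculoskeletal injury are all named risks in Section 8.1, so unless unusually severe or frequent they would fail that condition whatever their relatedness grade.
- For a serious event, Section 8.4 has the study psychiatrist notify the IRB without any relatedness condition, and unexpected serious events go to the IRB, program officer and Safety Officer within 48 hours.
- Event recording, the depression safety protocols (Section 8.2), psychiatrist oversight (Section 8.3) and review of severe and serious events (Section 8.5) do not depend on relatedness.

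These safeguards protect detection and response. They do not correct a relatedness grade that is too low.

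**Conclusion.** The point holds as a minor one. Factor 2 cannot be met by an effect that persists under continued dosing, and factor 1 cannot register worsening of a pre-existing symptom. The result is a possible downward pull on relatedness grades for sustained or worsening events, with consequences mainly where relatedness is a condition: the 2-week report, the 10-day report and discontinuation after a related serious event.

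The number of ratings affected cannot be estimated from the documents. The entry range on the screening depression scale might tempt a reader to size the problem, but Table 1 uses that scale only at telephone pre-screening. Depression during the study is followed with the PHQ-9, and factor 1 rests on what the participant reports. That range therefore says nothing about attribution.

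The conclusion assumes good compliance with daily dosing and the natural direction of each factor. The manual of procedures may give raters further guidance.

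**What to change.** In Section 8.4:

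- Reword factor 1: *whether the symptom is new, or has increased in severity or frequency from the baseline record (Relevant Symptoms, PHQ-9).*
- Reword factor 2: *whether the timing of onset or worsening relative to starting the powder is plausible, and, where doses were missed, stopped or restarted, whether the symptom improved or recurred; resolution within 24 hours of a dose is supporting evidence, and persistence during continued dosing does not count against relatedness.*

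Factor 2 should not be loosened to ask only whether onset or worsening fell within the intervention period. Practically every on-study event would meet that, and temporal association would become nearly automatic. Plausible timing and the response to interrupted dosing keep some discrimination.

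The cost is two reworded factors and a matching line on the adverse event form. No new data or visits are needed, and the sample size does not change. The downside is that some more events will be graded Possible.
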